5.4 Trial procedures**5.4.1 Screening**

Patients considered unsuitable for inclusion in this trial should be identified by their Investigator before the end of their participation in the preceding trial (i.e. should the investigator feel participation in the long term safety study is not in the patient's benefit or if the patient declines to participate in AK581) allowing adequate time for any alternative therapy to be implemented. The Investigators should discuss the suitability of patients to enter AK581 with the Sponsor at least four weeks before the likely time of entry in order that documentation, including ICF, can be put in place and continuity of drug supply can be ensured.

Ideally the patient will be entered on the long term safety trial on the last day of dosing of the parent trial on condition that they have provided consent.

5.4.2 *Dosing period(s)*

Patients will be dispensed drug at suitable timepoints during the trial

5.4.3 *Exiting the trial*

Patients may choose to leave the trial at any time or may be withdrawn by the Investigator in case of lack of efficacy, adverse reactions to rVA576 (Coversin), lack of compliance or for any other reason which, in the opinion of the Investigator, makes their continued participation no longer in their best interests.

Patients will also leave this trial, or an extended access trial if one is required, once rVA576 (Coversin) is fully approved and reimbursed for their indication in their country and once continuity of supply has been ensured.

5.4.4 *End of Study/Follow-up*

All patients will have a follow up clinic visit at 1 Month \pm 7 days and all women of child bearing potential (WOCBP) will have a follow up visit at Month 3 \pm 7 days from last dose.

Table 8: Schedule of Events for PNH Patients

EVENT (PNH)	Entry	ⁱ 1 Months (±7 days)	2 Months (±7 days)	3 Months (±7 days)	6 Months (±7 days)	9 Months (±7 days)	12 Months (±7 days)	15 Months (±7 days)	18 Months (±7 days)	21 Months (±7 days)	24 Months (±7 days)
Medical History. Eligibility & Informed Consent & demographics	✓										
ⁱⁱⁱ Physical Examination if not done within 7 days of entry	✓	✓	✓	✓	✓	✓	✓	✓	✓	✓	✓
^{iv} Vital Signs (including weight) at every visit	✓ ^{vii}	✓	✓	✓	✓	✓	✓	✓	✓	✓	✓
^v ECG	✓ ^{vii}						✓				✓
Urinalysis (including pregnancy testing) ^{viii}	✓ ^{vii}	✓	✓	✓	✓	✓	✓	✓	✓	✓	✓
ⁱⁱ Haematology & Chemistry including LDH, FBC and creatinine (local or central labs)	✓ ^{vii}	✓	✓	✓	✓	✓	✓	✓	✓	✓	✓

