6.2 Withdrawal criteria

In accordance with applicable regulations, a patient has the right to withdraw from the study at any time and for any reason, without prejudice to their future medical care by the physician or at the Institution. Should a patient withdraw from the study, then the patient will not undergo any further study-specific procedures or receive any treatment mandated by the protocol.

If a subject fails to attend scheduled trial assessments, the Investigator must determine the reasons and the circumstances as completely and accurately as possible.

In the event of the premature withdrawal of a patient from the trial, the end of trial visit should be carried out as completely as possible. Minimally, a safety assessment should be performed.

In the case of withdrawal due to the occurrence of unacceptable toxicity, the patient will be requested to remain under the supervision of the Investigator until the toxicity has resolved or is no longer considered to be clinically significant by the Investigator.

If an Adverse Event classified as severe results in patient withdrawal from the study, the subject will be followed until the AE (or SAE) resolves or stabilises, and any interventions required to resolve or stabilise the event will be recorded in the eCRF.

All withdrawals must be documented in the eCRF. A patient may be withdrawn in any of the following circumstances.

- Withdrawal of consent (mandatory withdrawal)
- Intake of non-permitted concomitant medication (may be discussed with the Sponsor and dependent on the nature of the medication)
- Patient is non-compliant with more than three consecutive missed doses and two missed clinic visits, in the opinion of the Investigator (discretionary withdrawal)
- If discontinuation is considered necessary by the Investigator and/or Sponsor (mandatory withdrawal)
- Request of Regulatory Agency (mandatory withdrawal)
- Patient develops an illness that would compromise his participation in the study (may be discussed with sponsor)
- Patient is not achieving complete inhibition at the maximum assigned dose (inadequate response to rVA576 (Coversin) treatment)
- Pregnancy, unless the patient wishes to consent to a termination.

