6.4 Compliance

Reasonable levels of compliance are assumed as a condition of entry (prior enrolment in and completion of a rVA576 (Coversin) clinical trial). As a measure of compliance, all empty rVA576 (Coversin) vials will be returned to the clinical unit and diary cards

will be reviewed by research staff. At the end of the study, all unused vials will be returned to the Sponsor or representative or destroyed at site.

In addition to the above measures, clinic staff may call the patient's home or set up an automated text message reminder according to the subjects dosing schedule.

Example text as follows: "A gentle reminder - please administer your medicine this morning/evening and record the time, dose and location of injection in the Patient Dosing Diary.

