3.5 Compliance and Exposure

Exposure will be derived as the number of days between the first and last dose of study medication in this study.

Study medication compliance will be derived as the proportion of doses that the patient received during the exposure period.

The overall patient compliance (%) will be derived as:

$$= 1 - (\text{Total number of missed doses} / \text{Total number of planned doses})$$

This derived compliance will be categorised:

- <95%
- 95% to <99%
- 99% to 100%
- >100%

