4.9 Study Drug Exposure and Compliance

Exposure to study medication, defined as the number of days between first and last dose (see section 3.5), will be summarized using descriptive statistics. In addition, a table will be provided to display the number and percentage of patients with exposure in the following categories:

- 1-182 days
- 183-365 days
- 366-730 days
- 731-1095 days

Study medication percentage compliance will be summarised using descriptive statistics. The count and percentage of patients with overall compliance will also be tabulated:

- <95%
- 95% to <99%

- 99% to 100%
- >100%

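### SAP compliance stops counting at the last dose, so doses missed between stopping and withdrawal drop out and a patient who gave up injecting can be tabulated as 99–100% compliant

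*SAP*

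**What the plan says.** SAP 3.5 sets the time window first: "Exposure will be derived as the number of days between the first and last dose of study medication in this study". It then ties compliance to that window: "Study medication compliance will be derived as the proportion of doses that the patient received during the exposure period". The formula that follows is one minus the ratio of missed to planned doses. Its numerator is given only as "Total number of missed doses", and the formula line does not repeat the window.

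SAP 4.9 gives the same definition of exposure ("Exposure to study medication, defined as the number of days between first and last dose (see section 3.5") and tabulates compliance in four bands: <95%, 95% to <99%, 99% to 100%, and >100%. The output is Table 14.3.7.

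The protocol foresees patients leaving because they stop dosing. Section 6.2 lists as a discretionary ground for withdrawal: "Patient is non-compliant with more than three consecutive missed doses and two missed clinic visits". Section 5.4.3 says that patients "may be withdrawn by the Investigator in case of lack of efficacy, adverse reactions to rVA576 (Coversin), lack of compliance". Section 6.4 names the data sources ("As a measure of compliance, all empty rVA576 (Coversin) vials will be returned to the clinical unit and diary cards", the latter reviewed by research staff) but gives no formula or window of its own.

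**The concern.** If the window closes at the last dose, the missed doses that precede a non-compliance withdrawal lie outside both the numerator and the denominator whenever the patient does not restart. Gaps after which the patient resumed are counted; the final gap is not. The error can run in one direction only, upward, and it is largest for patients who gave up.

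At stake is the reading of one descriptive table for a self-injected drug given for up to four years. A patient whose withdrawal reason in Table 14.1.1 is non-compliance could sit in the top compliance band of Table 14.3.7, with nothing in that table to explain why.

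**Working it through.** The documents report no compliance result, so there is no figure to reproduce. The check applies the SAP formula with two different window ends. The patients are illustrative assumptions: complete dosing up to the last dose, then no injections until withdrawal.

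**Inputs.** The formula, 1 − missed/planned, and the bands come from SAP 3.5. The 12-hourly and 24-hourly regimens come from protocol Table 7. The 3-monthly visits after Month 3 come from protocol Table 8.

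**One year of 12-hourly dosing, then 182 days off (about two visit intervals).**
- Doses taken: 365 × 2 = 730. Doses due afterwards: 182 × 2 = 364.
- Window to last dose: 1 − 0/730 = 100%, band 99% to 100%.
- Window to withdrawal: 1 − 364/(730 + 364) = 1 − 364/1094 = 66.7%, band <95%.
- Same gap, then one further dose: the gap is now inside the window, so the SAP's own rule gives 1 − 364/1095 = 66.8%. One injection moves the patient from 100% to 66.8%.

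**Two shorter cases.**
- Full dosing to Month 6, Month 9 and Month 12 visits missed, withdrawn at Month 12: 182.5/365 = 50% counted to withdrawal, 100% as written.
- Last dose 7 days before an early-termination visit at day 91: 84/91 = 92.3% counted to that visit, 100% as written.

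**Range, counted to withdrawal.** Every cell is 100% as written. Percentages are the same for 12-hourly and 24-hourly dosing.

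| Days on drug | 2 days off | 14 | 28 | 91 | 182 |
|---|---|---|---|---|---|
| 90 | 97.8% | 86.5% | 76.3% | 49.7% | 33.1% |
| 365 | 99.5% | 96.3% | 92.9% | 80.0% | 66.7% |
| 1095 | 99.8% | 98.7% | 97.5% | 92.3% | 85.7% |

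**Band thresholds.**
- In 365 days from first dose to withdrawal, 18 days off leaves 347/365 = 95.07%, still in the middle band; 19 days off gives 346/365 = 94.79%, below 95%.
- After 730 doses taken, 8 trailing missed doses give 730/738 = 98.9%, below 99%; 39 give 730/769 = 94.9%, below 95%.
- Four trailing missed doses, the smallest number that is more than three, give 730/734 = 99.5%, which stays in the top band. After a long exposure it is therefore the length of the gap, not the missed-dose trigger alone, that changes the band.

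**The case against.** The strongest reply has five parts.

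- **The text is not airtight.** The formula line sets no window for either total, so a programmer could count to withdrawal. That is true, but doing so would go against the sentence directly above it, and the ambiguity would itself need closing.
- **Persistence is visible elsewhere.** A reader might infer that compliance is the only tabulated evidence on whether patients keep injecting. The documents do not support that. SAP 4.9 summarises and bands exposure duration in the same table, SAP 4.6 summarises withdrawals with their primary reason, and the listings give patient-level detail. Someone who stops at Month 6 shows about six months of exposure. This objection stands and limits the importance of the point.
- **No objective or endpoint is affected.** A reader might also infer that the acceptability objective is compromised. SAP 2.1 assesses acceptability with named questionnaires, not with compliance. Compliance is not among the endpoints, no analysis set depends on it, and protocol 9.5 makes all analyses descriptive. This stands too.
- **Adherence while on treatment is a legitimate quantity.** It is, and a high value alongside a non-compliance withdrawal is not strictly a contradiction. But the table does not label it that way, and the rule treats identical gaps differently according to whether one more dose followed.
- **Data may be absent.** A patient who misses two visits may return no vials or diary for the gap, and protocol 9.6 and SAP 4.3 keep irretrievable missing data out of the analysis. This is a real difficulty, and any repair needs a stated rule for it.

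**Conclusion.** The point holds as a flaw in how one descriptive figure is defined. On the natural reading of SAP 3.5, trailing missed doses are excluded, and a patient withdrawn under protocol 6.2 can be tabulated at 99% to 100%. The bias is upward only. For an individual it ranges from negligible (99.8% against 100% for 2 days off after 1095 days) to large (33.1% against 100% for 182 days off after 90 days).

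The effect on the whole table is unknown. The documents give no expected number of such patients, and protocol 6.4 assumes reasonable compliance from completion of a parent trial. The individual figures assume complete dosing before the gap, no dosing during it, and withdrawal dated at its end. The primary safety endpoint, the secondary endpoints and the analysis sets are unaffected. The change is worth making because it is cheap, but the study's conclusions do not turn on it.

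**What to change.** In SAP 3.5:

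1. Count planned and missed doses from the first AK581 dose to the earliest of the documented decision to stop rVA576 (where recorded), the withdrawal or early-termination date, and the Month 48 visit. Doses not given after a documented decision to stop are then not counted as missed.
2. State that doses due in that window with no diary or vial evidence of administration count as not taken, report how many there are, and note this as an explicit exception to the missing-data rule in SAP 4.3.
3. Present investigator- or sponsor-directed interruptions separately.
4. Keep the first-to-last-dose figure alongside, labelled as compliance while on treatment.

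The work is SAP wording and programming. Protocol 6.2 requires withdrawals to be documented in the eCRF, and SAP Listing 16.2.1.3 shows visit dates. The documents do not show a field for the date of the decision to stop, which is why that anchor applies only where recorded. The downside is slightly lower reported compliance and an assumption about undocumented doses that may understate adherence in patients who injected but returned nothing. Showing both figures lets the reader see how much depends on it.

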3.6 Concomitant Medications

All medications recorded on the Concomitant Medications eCRF will be considered as used during the treatment period (i.e., concomitant).

All concomitant medication will be coded with Anatomical Therapeutic Chemical (ATC) class and preferred term.

3.7 Presentation

Statistical analyses will be performed using SAS[®] (Version 9.3 or later). All available data will be presented in patient data listings, which will be sorted by site number, patient identifier and where appropriate, visit and/or visit date.

Descriptive statistics (n, mean, standard deviation, median, first quartile, third quartile, minimum, and maximum) will be used to summarise the continuous efficacy and safety data. Discrete measures will be summarised using count and percentage. Unless otherwise stated, descriptive statistics showing the mean or median will be displayed to one decimal place more than the original data; the standard deviation will be displayed to two decimal places more than the original data; minimum and maximum will be displayed to the same number of decimal places as the original data.

Any significance tests or confidence intervals will be exploratory.

Unless otherwise stated, all data will be listed.

4 Statistical Methods Planned

4.1 Changes from Protocol

- ADA analyses may be performed at a later stage and results will be reported separately from the main CSR.
- The LDH categories referenced in the protocol were < 1.8, >1.8 to 2.4, >2.4 to 3, and >3 times the upper limit of normal (ULN), given that these do not cover LDH equal to 1.8ULN, the following categories will be used serum LDH ≤ 1.8, >1.8 to 2.4, >2.4 to 3, and >3 ULN

4.2 Analysis Sets

4.2.1 *Screened Set*

The Screened Set will include all patients screened for participation in the study.

4.2.2 *Full Analysis Set*

The primary analysis will be intention to treat and all patients who entered and signed informed consent will be included. The Full Analysis Set (FAS) will therefore include all enrolled patients.

All patients will be included in the safety analysis, whether completing the trial according to the protocol or not. Analyses of efficacy at various time points (6 months 12 months, 2, 3, 4 and 5 years) will be made for all patients reaching those points. The FAS will be the population used for assessing safety and efficacy and will be used for all outputs with the exception of patient disposition summary and data listings.

4.3 Review of Data and SAP Finalisation

Patient data will be reviewed for major protocol deviations by the Study Monitor during site visits and the entire team will review the database at timed intervals prior to the database lock.

Missing data that cannot be retrieved from source records or other repositories will be recorded as such in the eCRFs and will not be entered into the statistical analysis. Spurious data will be examined by the Sponsor's monitor, medical or statistical advisors and a decision made as to how it should be handled. If there is an obvious transcription or data entry error, such as a misplaced decimal point in a biochemical parameter, this will be discussed with the CRO or the laboratory and, if all parties agree, it will be corrected and endorsed by both the PI and the Sponsor.

Unused data (e.g. superfluous blood pressure recordings or haematological results in addition to those required by the protocol) will remain part of the source documentation and only be incorporated into the trial documents and analysis if there is reason for them to be (e.g. an unexpected fall in blood pressure that might constitute an AE).

The final analysis will be performed using data collected up to the end of the study. This data will be presented in the CSR.

4.4 Statistical Methods, definitions

4.5 General Data Handling Rules

Values from the locally reported laboratory will be converted to the standardised units at the SDTM level.

Laboratory values recorded as below the LLOQ or above the upper limit of quantification (ULOQ) will be handled as follows: results recorded as below will be imputed using half of the LLOQ for the purpose of calculating change from baseline, or percentage change from baseline, for summaries and figures. Measurements recorded as above the ULOQ will be imputed using the quantification limit. The raw data will be displayed in the listings.

The data may be log transformed, this will be guided by the degree of skewness and variability in the data within and between subjects across time.

4.6 Patient Disposition

Patient disposition will be provided for all screened patients, showing the number and percentage of patients who received study drug, completed the study visit schedule or withdrew early. For patients who withdraw from the study, the primary reason for the withdrawal will also be summarized.

The total number of patients who were screened and the number who failed screening will be tabulated. Screen failures and screen failure reasons will be listed in a data listing.

The number of patients Screened and the number and percentage of patients included in the FAS will be presented.

4.7 Demographics and Baseline Characteristics

Demographic characteristics will be summarized.

4.8 Medical History

Medical history findings at study entry will be summarized.

4.9 Study Drug Exposure and Compliance

Exposure to study medication, defined as the number of days between first and last dose (see section 3.5), will be summarized using descriptive statistics. In addition, a table will be provided to display the number and percentage of patients with exposure in the following categories:

- 1-182 days
- 183-365 days
- 366-730 days
- 731-1095 days

Study medication percentage compliance will be summarised using descriptive statistics. The count and percentage of patients with overall compliance will also be tabulated:

- <95%
- 95% to <99%

- 99% to 100%
- >100%

4.10 Concomitant Medications

The numbers and percentages of patients taking concomitant medications will be summarised by ATC and preferred term.

4.11 Analysis of Efficacy

All presentations and analyses of efficacy data will be conducted on the FAS. All efficacy data will be listed.

4.11.1 Blood Transfusions

The proportion of subjects who require PRBC transfusion during each 3-month period since the start of the study and over the entire period of the study will be summarised. This summary will also be produced by subgroup of patients based on their transfusions and complement inhibitor history as defined in section 3.2.4.

The number of RBC or platelet transfusions per patient during the study will be summarised using descriptive statistics. Patients with no recorded transfusions will be included with an imputed count of zero.

The time (days) to first transfusion for each patient will be summarized using Kaplan-Meier methodology. Kaplan-Meier estimates of the proportion of patients receiving at least one transfusion during the study will be displayed with 95% two-sided confidence limits. The median, 95% Confidence Interval of the median, 25th and 75th percentiles of the time to first transfusion will be produced.

4.11.2 LDH

The derived LDH ratio of reported:ULN values over time will be presented as a (spaghetti) line plot for all patients. Observed values and change from baseline will be summarised. Boxplots over time will also be presented to provide an indication of how the mean and median LDH ratio changes over the course of the study.

The number and percentage of patients with serum LDH \leq 1.8, >1.8 to 2.4, >2.4 to 3, and >3 times the upper limit of normal (ULN) at each 3-month time period since the start of the study will be summarised

The number and percentage of patients with median serum LDH \leq 1.8, >1.8 to 2.4, >2.4 to 3, and >3 times the upper limit of normal (ULN) over the entire duration of the study will also be summarised.

4.11.3 Transfusion-independence and Haemoglobin

The proportion of transfusion-independent subjects with haemoglobin (g/L) above the baseline haemoglobin value as defined in section 3.3.4 will be summarised at each 3-month time point.

The proportion of transfusion-independent subjects over the entire duration of the study with mean haemoglobin (g/L) above the baseline haemoglobin value as defined in section 3.3.4 will be summarised.

These summaries will be repeated separately for patients :

- i) transfusion-independent prior to receiving rVA576 (Coversin) and remain transfusion-independent
- ii) transfusion-dependent prior to receiving rVA576 (Coversin).

4.11.4 CH50

Observed values, change from baseline, and ratio to baseline expressed as a percentage (also called % activity) in CH50 will be summarised at each applicable study visit.

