3.1 Baseline (study entry) and Parent trial Baseline

In order to describe changes over time, and compare values to the pre-Coversin dosing value (historical baseline), some parameters (LDH, CH50, quality of life scores, haemoglobin) may have both parent trial baseline values and CONSERVE baseline values used in analyses. To avoid any confusion the term “baseline” will always refer to CONSERVE baseline, while ‘Parent trial baseline’ will be used otherwise.

Baseline will therefore be defined as the last measurement prior to CONSERVE study entry.

Parent trial baseline will be defined as :

- Baseline for CAPSTONE (AK580) defined as the value at which they received their qualifying transfusion (the set point)
- Baseline for COBALT (AK579) or CONSENT (AK578) the value at which patients entered those trials.

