3.3.3 CH50 Levels

Blood samples for CH50 will be collected as per the schedule of events and analysed in the Central Laboratory. The Central Laboratory considers values less than 10 CH50 U Eq/mL as completely inhibited. In previous trials (AK577, AK578 and AK579) with rVA576 (Coversin) the lower limit of quantification (LLOQ) of the CH50 was 8 CH50 EU/mL. The LLOQ has increased because the assay is now being performed using an automated system

for the ELISA. Results recorded as below the LLOQ will be imputed using half of the lower limit of quantification that applies to the sample for the purpose of calculating change from baseline, or percentage change from baseline, for summaries and figures.

The absolute change and percentage change from the parent trial Baseline to each subsequent assessment will be derived.

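### The SAP does not fix the denominator of CH50 % activity: read literally, SAP 4.11.4 uses the on-drug CONSERVE entry value, while SAP 3.3.3 uses the parent trial baseline

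*SAP*

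**What the plan says.** SAP 3.1 sets up two baselines. One purpose it gives is to "compare values to the pre-Coversin dosing value (historical baseline", and it notes that "some parameters (LDH, CH50, quality of life scores, haemoglobin) may have both parent trial baseline values and CONSERVE baseline values used in analyses". It then fixes the terminology: the unqualified word "will always refer to CONSERVE baseline", and "Baseline will therefore be defined as the last measurement prior to CONSERVE study entry".

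The derivation section for CH50, SAP 3.3.3, names the other baseline: "The absolute change and percentage change from the parent trial Baseline to each subsequent assessment will be derived". It also records that "The Central Laboratory considers values less than 10 CH50 U Eq/mL as completely inhibited" and imputes results below the LLOQ as half the LLOQ that applies to the sample.

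The analysis section, SAP 4.11.4, states that the "ratio to baseline expressed as a percentage (also called % activity) in CH50 will be summarised at each applicable study visit", with no qualifier on baseline. The titles of Tables 14.4.1.1 and 14.4.1.2 in SAP 7.1 add none.

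On patients' state at entry, Protocol section 4 has them join on the dose and frequency they had at the end of the previous trial. Inclusion criterion 3 in Protocol 4.1 asks for CH50 evidence of continuing inhibition but gives no cut-off.

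A related wording point concerns the parent baseline itself. SAP 3.1 has "Baseline for CAPSTONE (AK580) defined as the value at which they received their qualifying transfusion (the set point", without limiting it to one parameter. Secondary endpoint 8, in Protocol 3.2.1 and SAP 2.4.2, ties that set point to haemoglobin.

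**The concern.** A percentage called activity is naturally read as residual complement activity relative to the patient's own uninhibited level. If the denominator is a value taken on drug, the ratio measures drift since entry. A patient who is completely inhibited at entry and at the visit would then appear in a table as having 100% activity.

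A programmer who follows the terminology rule in 3.1 and one who follows the derivation in 3.3.3 would produce different tables from the same data. At stake is the readability of Table 14.4.1.2, the main tabular display of how well terminal complement inhibition is maintained.

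**Working it through.** The documents give no computed CH50 figure to reproduce, so the check applies each candidate denominator to the same visit result.

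**Inputs**
- LLOQ now 10 U Eq/mL; previously 8 in AK577, AK578 and AK579 (Protocol 5.5.1, SAP 3.3.3).
- Imputation below LLOQ: 10/2 = 5, or 8/2 = 4 under the earlier assay (SAP 3.3.3).
- Normal individual values: 58 to 156 U Eq/mL (Protocol 5.5.1). Using this range for an untreated parent value is an assumption.
- Visit result: below LLOQ 10, so imputed 5.

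**Formulas**, with B the baseline CH50
- % activity = 100 × 5/B
- percentage change = 100 × (5/B − 1)
- so, on a shared denominator, % activity = 100 + percentage change.

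| Denominator | B | % activity | Percentage change |
|---|---|---|---|
| CONSERVE entry, below LLOQ 10 | 5 | 5/5 = 100% | 0% |
| CONSERVE entry | 10 | 5/10 = 50% | −50% |
| CONSERVE entry | 20 | 5/20 = 25% | −75% |
| Parent, assumed untreated | 58 | 5/58 = 8.6% | −91.4% |
| Parent, assumed untreated | 156 | 5/156 = 3.2% | −96.8% |

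When entry is below LLOQ 10, the choice of denominator alone changes the result by a factor of 58/5 = 11.6 to 156/5 = 31.2.

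Loss of control is affected too. A visit value of 20 reads 20/5 = 400% against an entry value of 5, but 20/58 = 34.5% to 20/156 = 12.8% against the assumed parent range.

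**Limit of the parent denominator.** A patient switched from another complement inhibitor (group b in SAP 3.2.4) may have a parent value that is itself below LLOQ. The same visit then reads 5/5 = 100% (LLOQ 10) or 5/4 = 125% (LLOQ 8).

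**Same shorthand elsewhere.** Three other analysis sections also say baseline without a qualifier where section 3 names the parent trial baseline:
- LDH: 4.11.2 against 3.3.2.
- EORTC QLQ-C30: 4.11.5 against 3.3.4.
- EQ-5D-5L: 4.11.6 against 3.3.5.

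**The case against.** The best defence is that section 3 defines variables and section 4 only summarises them. SAP 3.3.3 is the only CH50-specific derivation and it names the parent trial baseline. The same shorthand for LDH, EORTC QLQ-C30 and EQ-5D-5L suggests that section 4 inherits its baselines from section 3. SAP 3.1 expressly permits both baselines for CH50, so two outputs on two baselines would not contradict each other. The stand-alone programming specifications announced in SAP section 6 may also name the denominator.

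This shows that the intended denominator may well be the parent value, and a change from CONSERVE entry is a legitimate summary in itself. It does not remove the ambiguity. SAP 3.1 states its terminology rule without exception, nothing in the SAP allocates a baseline to each CH50 output, and the table titles are silent.

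A reader might infer four stronger points that the documents do not support:
- **That the wrong denominator will be used.** The text shows an unresolved conflict, not a programmed error.
- **That 4.11.4 contradicts the search for more than 90% inhibition in SAP 3.4.10.** That section describes optional exploratory figures and does not tie inhibition to the 4.11.4 ratio.
- **That compassionate-use entrants will lack a parent baseline.** SAP 2.2 mentions such patients, but Protocol 3.1 and SAP sections 2 and 2.3 say that everyone comes from a parent trial.
- **That every entry value is an inhibited one.** Protocol 5.7.1 allows for a delay before entry, and Protocol 4.3.2 for treatment not continued during infection. An on-drug, inhibited entry value is the normal case, not a certainty.

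**Conclusion.** The conflict is real and minor. Under the literal reading, a completely inhibited visit can be tabulated as 100% activity, against 8.6% to 3.2% under the parent denominator. The first figure assumes an entry value below LLOQ 10. The second assumes an untreated parent value within 58 to 156, which may fail for switched patients.

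The consequences are limited. CH50 is an additional endpoint (SAP 2.5), the protocol makes all analyses descriptive (9.5), and Table 14.4.1.2 prints observed CH50 beside the ratio. The primary safety endpoint does not use it.

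The CAPSTONE set-point wording is a secondary point. Because 3.1 omits the restriction to haemoglobin, the parent baseline time point for LDH, CH50 and quality of life in CAPSTONE patients is unclear. A reader might infer that this distorts secondary endpoint 5, since EORTC QLQ-C30 and EQ-5D-5L changes are judged against that baseline. The documents do not show whether those measures were taken at the qualifying transfusion, so no such effect is shown.

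**What to change.** 1. In SAP 4.11.4 and Table 14.4.1.2, name the parent trial baseline as the denominator of % activity, in line with 3.3.3.
2. If a comparison with CONSERVE entry is also wanted, label it *change from CONSERVE baseline* and do not call it % activity.
3. Flag patients switched from another complement inhibitor, because the parent denominator does not cure a low parent value.
4. Show patients with no parent CH50 as not evaluable for % activity.
5. Name the baseline in the same way in 4.11.2, 4.11.5 and 4.11.6.
6. Reconcile the CAPSTONE definition in 3.1 with endpoint 8, and state the CAPSTONE parent baseline time point for LDH, CH50 and quality of life.

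The cost is SAP wording, table labels and some programming. Parent CH50 must come from the parent databases, which SAP 2.3 pools only where applicable and possible; CH50 is not among the parent items it lists for the AK581 casebooks. Item 4 covers the gaps, so no new data collection is needed.
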